16 APPENDIX D: ISOLATION AND CRYOPRESERVATION OF PERIPHERAL BLOOD MONONUCLEAR CELLS (PBMC)

A. Isolation of mononuclear cells by Lymphocyte Separation Medium (LSM) (Ficoll-Hypaque solution)

1. Place **fresh heparinized blood (not longer than 1 hour after drawing)** (approx. 15 ml) into a 50-ml conical centrifuge tube. Using a sterile pipet, add an equal volume of room-temperature PBS. Mix well.
2. Slowly layer the Lymphocyte Separation Medium (LSM) underneath the blood/PBS mixture by placing the tip of the pipet containing LSM at the bottom of the sample tube. Use 3 ml of LSM per 10 ml blood/PBS mixture.
3. Centrifuge 30 min. at 2000 rpm (900 xg), 18°C to 20°C, with no brake.
4. Using a sterile pipet, remove the upper layer that contains the plasma and most of the platelets. Using another pipet, transfer the mononuclear cell layer to another tube. Wash cells by adding excess Hanks balanced salt solution (HBSS) with 3X the volume of the removed supernatant. Resuspend cells in HBSS, and repeat the wash once to remove most of the platelets.
5. Resuspend mononuclear cells in RPMI-1640 medium containing 10% FCS. Count cells and determine viability by Trypan Blue exclusion.

B. Cryopreservation of PBMC

1. Prepare and label cryovials with patient #, cell concentration and date. (**It is best to have all vials labeled prior to pelleting of the cells**).
2. Aspirate supernatant.
3. Resuspend cells in a volume of formulate freezing medium to give desired concentration (approx 5-10 x 10⁶ cells/vial). **Please use Sarstedt Cryovial=0.5 and 2 ml screw cap Micro Tube ([name]; catalogue # 72.694.006).**

Preparation of Freezing media:

- (a) Measure out 45ml of **heat inactivated human AB serum** into a 50 ml centrifuge tube.
- (b) Add 5 ml DMSO to the tube.
- (c) Cap and invert tube for several times to mix.
- (d) If not all freezing media is to be used within 2 hours, aliquot extra portion into 15 ml centrifuge tubes and transfer to -20°C freezer for storage. Freezing media will expire one year after preparation.
4. Immediately dispense cells into the labeled cryovials ensuring that the cell concentration in each vial is labeled correctly.
5. Place full cryovials in a programmed freezer cooled to 4°C and begin the freezing at -1°C/min.
6. After freezing has been completed, transfer all vials to liquid nitrogen storage.

Abbreviated Title: Revlimid maintenance for MM

Version Date: 01/06/2017

17 APPENDIX E: COCKCROFT-GAULT EQUATION

(140-age [years])*(Weight [kg])*(0.85 if female) / 72 * serum creatinine [mg/dL]

Source: Cockcroft DW, Gault MH. Prediction of creatinine clearance from serum creatinine. Nephron 1976;16(1):31-41.

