2 ELIGIBILITY ASSESSMENT AND ENROLLMENT

2.1 ELIGIBILITY CRITERIA

2.1.1 Inclusion Criteria

- 2.1.1.1 Patients with multiple myeloma treated with induction therapy or re-induction therapy, who at the time of study enrollment have documented evidence of stable disease response or better according to International Myeloma Workshop Consensus Panel as provided in Section 6.2. The response assessment must occur at least 4 weeks after completion of their last treatment.
- 2.1.1.2 Age \geq 18 years. Because no dosing or adverse event data are currently available on the use of lenalidomide in patients $<$ 18 years of age, children are excluded from this study, but may be eligible for future pediatric trials.
- 2.1.1.3 ECOG performance status \leq 2 (see Appendix A).
- 2.1.1.4 Patient must have adequate hematologic, renal, hepatic, and cardiac function as defined by:
 - Absolute neutrophil count \geq 1.0K / μ L independent of growth factor support
 - Platelets \geq 75K/ μ L
 - Hemoglobin \geq 8 g/dL (transfusions are permissible)
 - Calculated creatinine (CrCl) clearance of greater than or equal to 40 mL/min. using the Cockcroft-Gault method (see Appendix E). If the calculated CrCl based on Cockcroft-Gault method is $<$ 40 mL/min, patient will have a 24 hr urine collection to measure CrCl. The measured CrCl must also be \geq 40 ml/min.
 - Total bilirubin \leq 1.5 mg/dL, AST (SGOT) and ALT (SGPT) \leq 3 x ULN
- 2.1.1.5 Females of childbearing potential (FCBP) must agree to use two effective forms of contraception simultaneously or to practice complete abstinence from heterosexual intercourse during the following time periods related to this study: 1) for at least 28 days before starting study drug; 2) while participating in the study; and 3) for at least

28 days after discontinuation from the study. The two methods of effective contraception must include one highly effective method (i.e. intrauterine device (IUD), hormonal [birth control pills, injections, or implants], tubal ligation, partner's vasectomy) and one additional effective (barrier) method (i.e. latex condom, diaphragm, cervical cap). FCBP must be referred to a qualified provider of contraceptive methods if needed.

- 2.1.1.6 A FCBP is defined as a sexually mature woman who: 1) has not undergone a hysterectomy or bilateral oophorectomy; or 2) has not been naturally postmenopausal for at least 24 consecutive months (i.e., has had menses at any time in the preceding 24 consecutive months).

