2.2 SCREENING EVALUATION

2.2.1 Clinical evaluation must be completed within 4 weeks prior to study enrollment:

A complete history and physical examination with documentation of type of response (sCR, CR, VGPR, PR, MR or SD according to criteria described in section 6.2) to induction or re-induction treatment, the time interval from last treatment to documentation of response, and assessment of performance status using the ECOG scale must be performed prior to study entry. Patients will be evaluated for baseline neuropathy.

Abbreviated Title: Revlimid maintenance for MM

Version Date: 01/06/2017

2.2.2 The following studies and laboratory tests will be completed within 4 weeks prior to study entry:

- 2.2.2.1 CBC with differential
- 2.2.2.2 Reticulocyte count
- 2.2.2.3 Acute care panel, calculated creatinine clearance using Cockcroft-Gault formula (within 2 weeks prior to study entry)
- 2.2.2.4 Mineral panel, Hepatic panel, Uric acid, LDH, and Beta-2 Microglobulin
- 2.2.2.5 PT, PTT
- 2.2.2.6 Serum protein electrophoresis (SPEP) and immunofixation to assess for presence and quantity of monoclonal protein (M-protein)
- 2.2.2.7 Random urine sample for protein electrophoresis (UPEP) and immunofixation to assess for monoclonal protein in the urine (Bence-Jones proteinuria). Collect a 24 hour urine sample if necessary for confirmation of multiple myeloma response to prior (re)induction treatment, or if calculated creatinine clearance is <40 ml/min.
- 2.2.2.8 Serum free light chain studies
- 2.2.2.9 Quantitative immunoglobulins
- 2.2.2.10 Viral serologies:
 - Hepatitis B surface antigen
 - Anti Hepatitis C (HCV) antibody. If positive, will follow with HCV RNA PCR
 - HIV ELISA screening test. If positive, will follow with confirmatory Western Blot test
- 2.2.2.11 Review of bone marrow core biopsy or aspirate
- 2.2.2.12 Serum or urine pregnancy test in women of child-bearing potential (complete within 10-14 days and again within 24 hours prior to prescribing lenalidomide for cycle 1)
- 2.2.2.13 12-lead EKG
- 2.2.2.14 Skeletal survey of the axial and appendicular skeleton. Exception may be made if skeletal survey has been performed within the past 3 months and was found to be positive. In this case, films will be forwarded to the Clinical Center for confirmatory interpretation by the Department of Radiology.

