3.3.4 Dose adjustments for Non hematologic toxicity

Lenalidomide Common Non-hematologic Toxicities	Dose Modifications
Non Blistering Rash	If Grade 3, hold lenalidomide, and restart at next lower dose level once rash improves to ≤ Grade 2.
Blistering, exfoliative or bullous rash (any grade), or suspected Stevens Johnson Syndrome (SJS) or Toxic Epidermal Necrolysis (TEN)	Discontinue lenalidomide and remove patient from therapy.
Venous or arterial thrombosis/embolism	Hold lenalidomide and start therapeutic anticoagulation. Restart lenalidomide at investigator's discretion at current or reduced dose level. Patient should continue anticoagulation therapy during the course of lenalidomide treatment. Additional work up to determine the cause of thromboembolic events may be done as clinically indicated at the discretion of investigator.
Renal Dysfunction CrCl based on Cockcroft-Gault formula: CrCl = (140 – Age) x Mass (in kilograms) x [0.85 if Female] 72 x Serum Creatinine (in mg/dL)	
 CrCl 31-60 ml/min – no dose modifications CrCl ≤30 mL/min (not requiring dialysis) – Dose reduce Lenalidomide to 10 mg every 48 hours CrCl ≤30 mL/min (requiring dialysis) – Decrease Lenalidomide to 5 mg daily and on dialysis days, dose lenalidomide after dialysis.
Other non-hematologic grade 3/4 toxicities judged to be related to lenalidomide. Readily reversible electrolyte and metabolic abnormalities or infections controlled by appropriate therapy are exempt.	Hold treatment and restart at next lower dose level when toxicity has resolved to ≤Grade 2

3.3.5 Monitoring (see study calendar for more specific details) Please Note: Day 1 may be delayed for up to one week for Cycle 2 and beyond.

3.3.5.1 Routine labs (CBC with diff, retic count, acute care panel, mineral panel, hepatic panel, LDH, uric acid) will be performed on Day 1 (within 3 days prior) and Day 15

Abbreviated Title: Revlimid maintenance for MM

Version Date: 01/06/2017

(within 3 days prior) of first cycle, on Day 1 (within 3 days prior) of cycles 2, 4 and 7 and on Day 1 (within 3 days prior) of every third cycle starting at cycle 10 at scheduled clinic visits, at the time of documented CR, and at disease progression (see study calendar).

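### Appendix E, cited by the 40 mL/min eligibility rule, leaves the Cockcroft-Gault denominator unbracketed; computed literally, clearance rises with creatinine, contradicting section 3.3.4

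*Combined protocol and SAP*

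**What the plan says.** Criterion 2.1.1.4 (section 2.1.1, Inclusion Criteria) requires a calculated clearance "greater than or equal to 40 mL/min. using the Cockcroft-Gault method (see Appendix E". If the calculated value is below 40, the "patient will have a 24 hr urine collection to measure CrCl", and the measured value must also reach 40. Section 2.2 (Screening Evaluation) lists "calculated creatinine clearance using Cockcroft-Gault formula (within 2 weeks prior to study entry" without repeating the formula.

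Appendix E gives the formula on a single line, which ends "0.85 if female) / 72 * serum creatinine [mg/dL". The age, weight and sex terms are each bracketed. The two terms after the slash are not.

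Section 3.3.4 (renal dysfunction row) states the same formula a second time. The text runs "x [0.85 if Female] 72 x Serum Creatinine (in mg/dL", with no operator between the sex factor and 72. That fits a stacked fraction with 72 times creatinine as its lower line. The rows beside it treat low clearance as the abnormal state, down to patients on dialysis.

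**The concern.** Division and multiplication have equal precedence and are evaluated from left to right. A spreadsheet, statistical package or database field given the Appendix E line as typed would divide by 72 and then multiply by creatinine. The estimate would then move in the wrong direction, with higher creatinine producing higher clearance.

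The line matters because it is the one the eligibility criterion cites. The 24-hour urine collection does not guard against the error: for clearance it is triggered only by a calculated value below 40, and the literal reading inflates the value in the patients with high creatinine. Section 1.2 lists renal insufficiency among the features of myeloma, so raised creatinine is foreseeable in this population.

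**Working it through.** The plan gives no worked clearance value, so there is no figure of its own to reproduce. The check evaluates the printed line in its two possible readings.

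**Inputs from the documents.** The formula terms come from Appendix E, the limit of 40 mL/min from 2.1.1.4, and the second statement of the formula from 3.3.4.

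**Inputs assumed.** The documents give no example patient. Ages, weights, sexes and creatinine values below are assumptions chosen for illustration.

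**Formulas.** Let K = (140 − age) × weight × sex factor / 72, and let S be serum creatinine in mg/dL.

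- Literal reading, left to right: K × S
- Grouped reading, with 72 × S as the denominator: K / S
- Ratio of literal to grouped: (K × S) / (K / S) = S²

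The ratio depends on neither age, weight nor sex. The two readings agree only at S = 1.0.

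**Man aged 65, 75 kg (assumed).** K = (140 − 65) × 75 / 72 = 5625 / 72 = 78.1.

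| Creatinine (mg/dL) | Grouped (mL/min) | Literal (mL/min) | Ratio | Meets 40: grouped / literal |
|---|---|---|---|---|
| 0.5 | 156.2 | 39.1 | 0.25 | yes / no |
| 0.8 | 97.7 | 62.5 | 0.64 | yes / yes |
| 1.0 | 78.1 | 78.1 | 1.00 | yes / yes |
| 1.5 | 52.1 | 117.2 | 2.25 | yes / yes |
| 2.0 | 39.1 | 156.2 | 4.00 | no / yes |
| 3.0 | 26.0 | 234.4 | 9.00 | no / yes |

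The grouped form meets the limit when S ≤ K / 40 = 78.125 / 40 = 1.95. The literal form meets it when S ≥ 40 / K = 40 / 78.125 = 0.51. For this man the two readings give opposite decisions above 1.95 and below 0.51.

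**Range over other assumed patients.**

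- Woman aged 75, 60 kg: K = 65 × 60 × 0.85 / 72 = 46.0. At S = 2.0, grouped is 23.0 and literal is 92.1. At S = 0.8, grouped is 57.6 (meets the limit) and literal is 36.8 (does not).
- Man aged 55, 90 kg: K = 85 × 90 / 72 = 106.2. At S = 2.0 both readings meet the limit (53.1 and 212.5). At S = 3.0, grouped is 35.4 and literal is 318.8.

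Across these three patients the highest creatinine that meets the limit under the grouped form runs from 46.04 / 40 = 1.15 to 106.25 / 40 = 2.66 mg/dL.

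**Which reading the documents support.** In 3.3.4, 72 × S stands as one unit after the numerator, and low clearance is labelled renal dysfunction. Clearance must therefore fall as creatinine rises, which only the grouped form does.

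**The case against.** The strongest reply is that this is a slip of notation and not a different rule. The criterion is defined by a named method, "using the Cockcroft-Gault method (see Appendix E" being only a pointer, and the précis and section 2.2 name the method without citing the appendix. Appendix E carries the method's name and its source. A reader who takes everything after the slash as the denominator gets the intended result, and 3.3.4 shows the direction. Literal output would also look odd: 234 mL/min at a creatinine of 3.0, or 39 at 0.5, is likely to be noticed by staff screening for renal function. Nothing in the documents describes a worksheet, case report form or program built from the Appendix E line.

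All of that stands, and it limits the practical risk. It does not make the printed line correct, and the line is the one cited for an eligibility threshold.

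A second reply is that layout may have been lost when the PDF was read. In 3.3.4 no fraction bar or division sign survives, so its stacked form is inferred. The same loss in Appendix E cannot be fully excluded. It is unlikely, because the slash, the asterisks and the other brackets are all present there, and a displayed fraction in section 5.2 (the lysis formula) came through intact. The page itself will settle it.

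A reader might infer that the protocol applies a wrong clearance rule, or that patients with poor renal function were in fact enrolled. The documents support neither: they show how the line is printed, not how anyone calculated from it.

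**Conclusion.** The point holds as an unbracketed denominator in an operational formula. Read in standard operator order, Appendix E contradicts 3.3.4 and reverses the relation between creatinine and clearance. The error factor is creatinine squared for every patient: fourfold too high at 2.0 mg/dL, ninefold at 3.0, and 0.64 of the grouped value at 0.8. The individual clearance values rest on assumed patients; the direction and the factor do not.

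The consequence is conditional on literal computation or coding. Under that condition, patients with high creatinine could pass the 40 mL/min limit without the 24-hour urine check, and some with low creatinine could be flagged below it.

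It might also be inferred that the clearance bands in 3.3.4 are compromised. They are not shown to be, because that section prints its own formula and does not depend on Appendix E. Creatinine clearance does not enter the paired comparisons or the power statement in section 8.1, so the primary analysis and power are unaffected. The correction is worth making because the text sits behind an eligibility threshold, but it is a small one.

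**What to change.** Write Appendix E with an explicit denominator:

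[(140 − age) × weight × (0.85 if female)] / (72 × serum creatinine)

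Check on the page that 3.3.4 shows its fraction clearly, so that the two statements match. Confirm that any eligibility worksheet or database calculation in use has the grouped form. If one was coded literally, recompute the screening clearances from the recorded age, weight, sex and creatinine.

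The cost is one pair of brackets and a short check of any calculation tool. The 40 mL/min limit, the urine-collection rule and all dosing text stay as they are.

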18 APPENDIX F: BONE MARROW ASPIRATE COLLECTION, SORTING AND STORAGE

Collection of Bone Marrow

- Refer to section **5.1** for biomarker study bone marrow timepoints and study calendar section **3.4**
- Orders for bone marrow biopsies should be placed in the Clinical Research Information System (Clinical Research Center, NIH, Bethesda, MD).
- Notify the CCR Hematology lab that flow immunophenotyping is being performed [contact]). The hematology BM collection tech will bring a 10 mL tube sodium heparin Vacutainer tube to the specimen collection site and prepare an extra smear for the Flow Cytometry Laboratory.
- Get sterile heparin suitable for injection from the nurse's station. Rinse syringe and needle with sterile heparin, leaving no less than 0.5 mL in syringe.
- Bone marrow samples will be collected as bone marrow core biopsies and aspirates for analyses. Aspirate first 2 cc of marrow for morphology first and give specimen to CCR Hematology lab technician to be given to CCR Pathology department (1 mL will go to Hematopathology and 1 mL will be delivered to [name] for research assessing proteasomes). Reposition needle and, for cellular specimens, slowly aspirate 5-8 mL of bone marrow for flow cytometry and cell sorting.
- Bone marrow core biopsies and one fraction of marrow aspirates will be fixed and paraffin-embedded for histological/immunohistochemical analysis and long term storage. One fraction of marrow aspirates will be stored as air-dried aspirate smears and the rest will be frozen.
- For aspirate specified for flow cytometry under the direction of [name], immediately discharge 1 mL of aspirated marrow syringe into a 10mL sodium heparin Vacutainer, cap tube tightly and mix by gentle inversion 5-6 times. Label tube with patient name, unique identifier number and date. Deliver immediately to the Flow Cytometry Laboratory B1B58 (specimens containing hematopoietic neoplasms have a tendency to clot and must be processed immediately). Call for STAT Escort pickup and delivery if you cannot deliver the specimen yourself [contact]).
- For aspirate designated for sorting, GEP profiling, microenvironment studies, send remaining aspirate sample to the Lymphoid Malignancies Branch lab. For questions regarding these samples, please contact [name] at [contact]. Place aspirate sample in EDTA syringe immediately on ice. Transfer within 30 minutes of sampling to the lab for processing.
